8.2.2 Cycle 2-12 Assessments (for dosing administered on Days 1 and 15)

Laboratory evaluations must be completed within 7 days prior to Day 1 and Day 15 of each cycle, while interval history and physical exam must occur within 7 days prior to study agent administration. See [Appendix I](#) for full details. Dosing should occur on days 1 and 15 of each cycle but may be delayed up to 48 hours if necessary. Doses delayed by more than 48 hours but less than 28 days due to toxicity or otherwise, require resetting the treatment schedule as outlined in protocol [Section 5.6](#). Clinical assessments to be done on Day 1 of each subsequent cycle to include assessment of the following at each visit unless otherwise specified:

8.2.2.1 KS tumor assessment to be completed on Day 1 of each cycle. Response of KS to treatment is described in [Section 9.1](#). Photographic documentation will be completed at each visit when the KS response category changes ([Appendix VI](#)).

8.2.2.2 A complete physical exam including: vital signs, weight, toxicity assessment, and ECOG or KPS performance status. See [Section 8.2.1.3](#) for BP measurement instructions. See [Section 5.4](#) for special considerations for participants with cardiac risk factors and specific instructions for participants who develop \geq grade 2 hypertension while on treatment. On Day 15, only vital signs including weight will be performed.

8.2.2.3 If HIV positive, assessment of adherence to antiretroviral therapy.

8.2.2.4 Review of concurrent medications, including antiretroviral therapy.

8.2.2.5 If HIV-positive, all HIV-related and AIDS-defining events ([Appendix V](#)).

8.2.2.6 Review of signs and symptoms. Imaging, as appropriate, for suspected visceral KS or for follow-up of visceral KS is at the discretion of the investigator.

- 8.2.2.7 CBC with differential on Days 1 and 15.
- 8.2.2.8 Serum chemistries: electrolytes (sodium, potassium, chloride, bicarbonate, calcium, phosphorus, glucose), total protein, albumin, liver enzymes (AST (SGOT), ALT (SGPT), alkaline phosphatase), BUN, creatinine, bilirubin (direct and indirect) on Days 1 and 15.
- 8.2.2.9 Urinalysis for proteinuria on Day 1.
- 8.2.2.10 Biologic endpoints: peripheral blood for biologic endpoints described in [Appendices I](#) and [III](#) will be collected at Day 1 of Cycles 2, 4, 6, 7, and 10. The samples include blood for immune studies on Day 1 of Cycles 2, 4, and 6 to be done before study treatment dosing. Given this will be a fresh blood sent at room temperature overnight, if the blood for immune studies cannot be collected on Monday-Wednesday (i.e., the dose is administered on Thursday or Friday), this blood work can be obtained the Monday AFTER the dose was given. Blood for HHV-8 viral loads and archived research purposes on Day 1 of Cycles 4, 7, and 10, and at treatment discontinuation.
- 8.2.2.11 Biologic endpoints: peripheral blood for pharmacokinetics as described in [Appendices I](#) and [II](#) will be collected on Day 1 and 15 of Cycle 2; the samples will be drawn pre-dose.
- 8.2.2.12 If HIV positive, T-lymphocyte subsets (CD4 and CD8) to be done every three cycles (Day 1 of Cycle 4, 7, and 10), and at treatment discontinuation.
- 8.2.2.13 If HIV positive, HIV-1 plasma RNA to be done every three cycles (Day 1 of Cycles 4, 7, and 10), and at treatment discontinuation).
- 8.2.2.14 FAHI+KS quality of life questionnaire on Day 15 of Cycle 4 (questionnaire may be performed up until Day 15 of Cycle 5). Those who have HIV-negative KS will not have the HIV portion scored. See [Appendix XII](#) for KAH1+KA questionnaire.

8.3 Treatment Discontinuation

At the time of treatment discontinuation, all evaluations should be completed as soon as possible. AEs must be reported to the AMC Operations and Data Management Center if the AE began any time within 4 weeks of receiving the study treatment. Additionally, if a site learns of any incidence of death, cancer, or fetal anomaly, which is possibly, probably, or definitely related to the drug, at any time after treatment discontinuation, the event should be reported to the NCI through CTEP-AERS (see [Section 6.3](#)) within 24 hours of when the investigator learns of the event. This information may provide additional insight into the safety of sEphB4-HSA.

The following procedures should be performed upon discontinuation of study drug:

- CBC with differential.
- Serum chemistries: liver enzymes (AST [SGOT], ALT [SGPT], alkaline phosphatase), BUN, creatinine, electrolytes (sodium, potassium, chloride, bicarbonate, calcium,

phosphorus, glucose), total protein, albumin, bilirubin (direct and indirect).

- Complete physical examination including: vital signs, weight, ECOG or KPS performance status, signs and symptoms review, and toxicity evaluation.
- Review of antiretrovirals and adherence to antiretroviral therapy (if applicable).
- Review of AIDS-defining events.
- KS tumor assessment with photographic records. Response of KS to treatment with sEphB4-HSA will be assessed as described in [Section 9.1](#).
- KS staging ([Appendix VII](#)).
- Biologic endpoints: peripheral blood for biologic endpoints including HHV-8 viral load and peripheral blood for archive research purposes.
- If HIV positive, CD4 and CD8 counts and percentages, quantitative HIV-1 plasma RNA.
- Urinalysis.
- If the participant had documentation of visceral disease while on study, re-evaluation of visceral disease, if not already done while on study. This should be done before the post-treatment evaluation.
- Permanent discontinuation of drug will be documented.

8.4 Post-treatment Evaluation

All participants must be seen 4-6 weeks after discontinuation or completion of study treatment (counting from Day 28 of the final cycle). If participants are unable to return to the clinic, attempts should be made to obtain follow-up information from the treating physician regarding performance status, tumor status, toxicity, and subsequent care. Participants who withdraw for toxicity reasons should be followed until the toxicity resolves/returns to baseline, or for at least 4 weeks, whichever is later. In addition, participants who go off treatment for reasons other than toxicity should be followed for at least 4 weeks after discontinuing drug.

The following procedures should be performed during the post-treatment evaluation visit:

- CBC with differential.
- Serum chemistries: liver enzymes (AST [SGOT], ALT [SGPT]), alkaline phosphatase, BUN, creatinine, electrolytes (sodium, potassium, chloride, bicarbonate, calcium, phosphorus, glucose), total protein, albumin, bilirubin (direct and indirect).
- Complete physical examination including: vital signs, weight, ECOG or KPS performance status, signs and symptoms review, and toxicity evaluation (AEs must be reported per [Section 6.4](#)).
- Review of AIDS-defining events.
- KS tumor assessment with photographic records if there are any changes from the treatment discontinuation visit. Response of KS to treatment with sEphB4-HSA will be assessed as described in [Section 9.1](#).

- KS staging ([Appendix VII](#)).
- If the participant had documentation of visceral disease while on study, documented re-evaluation of visceral disease.
- FAHI+KS quality of life questionnaire ([Appendix XII](#)). Those who have HIV-negative KS will not have the HIV portion scored.
- At a participant's final study visit the Off-Study Summary Form will be completed.

Telehealth follow-up visits are permitted in the event an in-person visit is restricted and a response evaluation is not required at that visit. The complete physical examination will be deferred (i.e., vital signs, physical); however, symptoms review, and AIDS-defining events review will be conducted via teleconference. If there is any concern of progression or symptoms related to progression of KS, an in-person visit is required to follow the telemedicine visit within 2 weeks.

8.5 Follow-up Visits

All participants achieving PR, or CR will have additional physical exams repeated every 3 months (counting from, Day 28, of the final cycle), for up to 1 year or until an earlier time of disease progression requiring additional treatment. AEs must be reported to the AMC Operations and Data Management Center if the AE began any time within 4 weeks of receiving the study treatment. Additionally, if a site learns of any incidence of death, cancer, or fetal anomaly, which is possibly, probably, or definitely related to the drug, at any time after the study is closed, the event should be reported to the NCI through CTEP-AERS (see [Section 6.3](#)) within 24 hours of when the investigator learns of the event. This information may provide additional insight into the safety of sEphB4-HSA.

The following procedures should be performed during the follow-up visits:

- Complete physical examination including: vital signs, and signs and symptoms review.
- Review of AIDS-defining events.
- KS Tumor Assessment (without photographs).
- At a participant's final study visit the Off-Study Summary Form will be completed.

Telehealth follow-up visits are permitted in the event an in-person visit is restricted. The complete physical examination will be deferred (i.e., vital signs, physical); however, symptoms review, and AIDS-defining events review will be conducted via teleconference. If there is any concern of progression or symptoms related to progression of KS, an in-person visit is required to follow the telemedicine visit within 2 weeks.

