9.1.9 Response duration

Response duration is defined as the time from first documentation of response to documentation of first progression.

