- ^r Photographs to be obtained when the KS response category changes
- ^s Includes vital signs (temperature, pulse, BP, respiratory rate), height (baseline only), weight. For cycles 2-12, only vital signs and weight are to be collected on Day 15.
- ^t Includes liver enzymes (AST (SGOT), ALT (SGPT), alkaline phosphatase), BUN, creatinine, electrolytes (sodium, potassium, chloride, CO₂, calcium, phosphorus, glucose), total protein, albumin, bilirubin (direct and indirect)
- ^u Participant must be on a stable antiretroviral regimen for at least 12 weeks prior to study entry.
- ^v QTcF (Fridericia Correction Formula) > 480 on 2 out of 3 EKG's (if first EKG is < 480, no need to repeat; if first EKG is > 480, repeat twice for a total of 3 EKG's)
- ^w Negative, Trace, or 1+ protein: continue with sEphB4-HSA; ≥ 2+, see [Section 5.3](#) for dosing changes
- ^x No photographs needed.
- ^y Must be obtained on Sunday-Thursday.
- ^z Must be obtained on Monday-Wednesday.
- ^{aa} If scheduled day is Fri-Sat, please obtain sample 7 days before or after scheduled day to be mailed express overnight on a Sunday-Thursday.
- ^{bb} Hypertension is an expected adverse event within the class of anti-neoplastic drugs affecting the vascular endothelial growth factor (VEGF) pathway. In participants with a baseline blood pressure (BP) ≥ 120/80 mm Hg and cardiac risk factors (history of hyperlipidemia, smoking, diabetes, treatment for hypertension, African-American ethnicity),⁶⁷ hypertension should be anticipated and therefore may need more aggressive management *prior to* first dose of study drug. In these cases, it is recommended that an internal medicine specialist or cardiologist be consulted to assist in management of hypertension. See [Section 5.4](#) for specific instructions for titration of antihypertensive drugs for those with cardiac risk factors, as well as specific instructions for participants who develop ≥ grade 2 hypertension while on treatment. See [Section 8.2.1.3](#) for BP measurement instructions.

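### Section 8.5 lets a telehealth contact stand in for a scheduled responder tumor assessment with no make-up assessment, so off-treatment progression can be documented late or missed and response duration can be lengthened.

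*Combined protocol and SAP*

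**What the plan says.** Section 8.5 applies only to participants with PR or CR. It calls for "additional physical exams repeated every 3 months", for up to 1 year or until earlier progression that needs further treatment. The listed procedures include a tumor assessment ("KS Tumor Assessment (without photographs"). Appendix I schedules the same assessment in its follow-up column, with the footnote "No photographs needed".

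The telehealth provision in 8.5 reads "Telehealth follow-up visits are permitted in the event an in-person visit is restricted". The physical examination is then deferred, and "symptoms review, and AIDS-defining events review will be conducted via teleconference". If there is any concern about progression, or symptoms related to it, "an in-person visit is required to follow the telemedicine visit within 2 weeks".

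Section 8.4, on the post-treatment visit, has the same provision with one more condition: "Telehealth follow-up visits are permitted in the event an in-person visit is restricted and a response evaluation is not required at that visit". It has the same 2-week rule.

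Section 9.1.4 defines cutaneous progression by lesion diameters, lesion counts and raised-lesion counts. Section 9.1.9 states: "Response duration is defined as the time from first documentation of response to documentation of first progression". Section 10.1 plans Kaplan-Meier estimates of time to response, relapse and death, and repeats the definitions of time to progression and response duration. It does not say how a visit without a tumor assessment enters these analyses, or where a participant without documented progression is censored.

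**The concern.** The condition that protects tumor assessment in 8.4 is absent from 8.5, where the visits are for responders only and progression after response is the event of interest. A site that follows 8.5 as written can complete a scheduled visit by telehealth, do no tumor assessment, and owe none before the next visit.

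After treatment ends, these visits are the main scheduled source of progression dates. Participants with CR stop after one further cycle, so much of their follow-up falls here. Response duration ends on the date when progression is documented, so late documentation lengthens it by definition. Follow-up visits have no photographs from which an earlier date could be recovered. At stake is the dating of off-treatment relapse and progression in a small group of responders.

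**Working it through.** **The plan's own figures.** With 20 participants, at least 9 responders and at most 3 with unacceptable toxicity, and response and toxicity taken as independent:

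- Power = P(X ≥ 9 | 20, 0.60) × P(T ≤ 3 | 20, 0.10) = 0.9435 × 0.8670 = 0.818 (stated 0.82).
- Significance level = P(X ≥ 9 | 20, 0.30) = 0.113 on the response edge and P(T ≤ 3 | 20, 0.30) = 0.107 on the toxicity edge (stated 0.11).

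Both figures reproduce, and neither depends on the 8.5 visits.

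**Visit gaps.** 12 months / 3 months = 4 follow-up assessments. If one is replaced, the gap between neighbouring follow-up assessments grows from 3 to 6 months, and documentation can be up to 3 months later. Two in a row give a 9-month gap and up to 6 months of added delay. If the month-12 visit is replaced, no scheduled visit remains to find the progression.

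**Illustration.** The documents give no telehealth frequency, no relapse rate and no yield for the 2-week rule, so all three are assumptions. Take exponential time to progression from the start of follow-up, visits at 3, 6, 9 and 12 months, a share q of visits by telehealth, and a share s of progressions noticed on the call and confirmed in person 2 weeks later. A progression passes a visit undocumented with probability r = q(1 − s).

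With a true median of 6 months, the chances of progressing in the four intervals are 0.2929, 0.2071, 0.1464 and 0.1036 (total 0.75). The share missed by month 12 is

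(0.2929 r⁴ + 0.2071 r³ + 0.1464 r² + 0.1036 r) / 0.75.

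For q = 0.5 and s = 0, r = 0.5: (0.0183 + 0.0259 + 0.0366 + 0.0518) / 0.75 = 0.1326 / 0.75 = 17.7%. If telehealth contacts count as progression-free, the recorded share without progression at month 12 is 0.25 + 0.1326 = 38.3%, against a true 25%. The mean delays below come from a simulation under the same assumptions.

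| Visits | Noticed on call (s) | Missed by month 12 | Recorded progression-free at month 12 | Mean delay (months) |
|---|---|---|---|---|
| All in person | – | 0% | 25.0% | 1.6 |
| Half telehealth | 0 | 17.7% | 38.3% | 3.2 |
| Half telehealth | 0.5 | 5.3% | 28.9% | 2.5 |
| Half telehealth | 0.8 | 1.6% | 26.2% | 2.1 |
| Half telehealth | 1 | 0% | 25.0% | 1.8 |

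With a quarter of visits by telehealth and s = 0, r = 0.25 and 5.3% are missed. With half by telehealth and s = 0, the missed share is 15.3% for a true median of 4 months and 19.5% for 9 months.

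**Medians.** For a true median of 4 months, the all-in-person curve reaches 35.4% at month 6, so the recorded median is 6 months. With half telehealth and s = 0, it stands at 57.5% at month 6 and 39.3% at month 9, so the recorded median is 9. With s = 0.5 it falls below one half two weeks after the month-6 visit (about 6.5 months). For a true median of 6, the all-in-person curve stands at exactly 50% at month 6, so the recorded median is unstable there and the month-12 share is the better summary.

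**Dependence on the censoring rule** (true median 6, q = 0.5, s = 0), Kaplan-Meier at months 6, 9 and 12:

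- All in person: 50.0%, 35.4%, 25.0%.
- Telehealth counted as progression-free to month 12: 67.7%, 51.5%, 38.3%.
- Censored at the last in-person assessment: 64.4%, 43.9%, 21.3%.

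Late dating raises the curve at months 6 and 9 under either rule. At month 12 the direction depends on the rule.

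**The case against.** The strongest reply is the 2-week rule. It is triggered by any concern or by symptoms, and it has a deadline. Every participant has skin disease, which the background section describes as visible, so many will notice a change themselves. The table bears this out: at half noticed, the missed share falls from 17.7% to 5.3%. What stands against it is that the trigger is suspicion, while 9.1.4 turns on counts and measurements. Section 8.4 has the same rule and still adds its condition.

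Second, telehealth is allowed only when an in-person visit is restricted. The alternative on that date may be no visit at all, so part of the gap comes from the restriction, and the call adds some chance of detection. That is fair, and it is why telehealth should stay. It does not explain why no make-up assessment is required. The examination is called deferred, but no date is set.

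Third, the reach is limited. PR participants may be assessed on treatment for up to 12 cycles, with tumor assessment on Day 1 of each. Recurrence after CR is the appearance of tumor (9.1.6), which is easier to notice than a 25% change. Response duration is in none of the stated objectives. All of this stands, and it keeps the point minor.

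A reader might infer that progression will be missed and response duration will be overstated. The documents do not support that. They do not say that a telehealth contact counts as a progression-free assessment, and the net direction depends on a censoring rule that is not written. A reader might also take about 9 responders as the expected number. Nine is the minimum for rejection; the alternative of 0.60 implies 0.60 × 20 = 12.

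**Conclusion.** The point holds as a gap in the plan. Section 8.5 allows a scheduled responder tumor assessment to be replaced by a contact that contains none, with no make-up, and 10.1 does not say how that contact is analysed. Progression that raises no concern or symptoms on the call can be documented about 3 months late for one substitution and up to 6 months late for two in a row, or missed within the 1-year follow-up. Recorded response duration and time to progression or relapse can be lengthened, most clearly if telehealth contacts are treated as progression-free.

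The size rests on assumptions about telehealth use, noticing on the call and relapse rate. With half the visits by telehealth and true medians of 4 to 9 months, the missed share runs from 0% to about 19%. With little telehealth or good noticing, the effect is small. The primary response and toxicity endpoints, the 9/3 rule, and the stated power and significance level are unaffected. The change is desirable and cheap, but not critical.

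**What to change.** In 8.5, keep telehealth and add: a telehealth visit does not replace the KS Tumor Assessment, which is to be done in person at the earliest possible date before the next scheduled visit. The final follow-up visit has no next visit, so the sponsor should set a latest date for it.

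In 10.1, add: telehealth contacts are not tumor assessments, and participants without documented progression are censored at their last in-person KS assessment. Both sentences are needed. The last comparison in the working shows that the censoring rule alone does not remove late dating.

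The 8.4 condition should not simply be copied into 8.5. Every 8.5 visit lists a tumor assessment, so a literal copy could remove telehealth from these visits altogether.

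The cost is one sentence in each section, plus a date for the last visit. Some visits must be rescheduled, and some response durations will be censored earlier. No new procedure is added, because the assessment is already scheduled.

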9.0 MEASUREMENT OF EFFECT

All participants will be evaluated for response by physical examination on Day 1 of every cycle (± 3 days). See [Appendix I](#) for the KS Tumor Assessment schedule.

CTEP-registered physician investigators and CTEP-registered advanced practice clinicians who are non-physician investigators (i.e., NP or PA) may perform toxicity and response assessment per local licensure requirements.

Evaluable for toxicity:

All participants will be evaluable for toxicity from the time of their first treatment with sEphB4-HSA. For the primary toxicity endpoint, we will report toxicities occurring during the first two cycles of therapy.

Evaluable for objective response:

Only those participants who have measurable disease present at baseline, have received at least two cycles of therapy, and have had their disease re-evaluated will be considered evaluable for response. These participants will have their response classified according to the definitions stated below (Note: Participants who exhibit objective disease progression prior to the end of Cycle 1 will also be considered evaluable.). For the primary efficacy endpoint, we will report the clinical response (CR or PR) rate after 2 or more cycles of treatment. Participants with KS which progress prior to the end of Cycle 2 will be considered to have treatment failure.

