3.3 Number of Participants to be Enrolled

3.3.1 Proposed sample size

This study will enroll a minimum of 6 participants and a maximum of 20 participants.

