10.2 Sample Size/Accrual Rate

A total of 20 evaluable participants will be enrolled. The design was developed by considering the joint probability of clinical response and toxicity simultaneously (Jin H. Alternative designs of phase II trials considering response and toxicity, *Contemp Clin Trials* 28 (2007): 525-53). The null hypothesis for defining the unacceptable region based on clinical response rate and toxicity rate simultaneously and the alternative hypothesis for defining the region for a promising agent are as follows:

- $H_0: P_{\text{resp}} \leq 0.30 \text{ OR } P_{\text{tox}} \geq 0.30$
- $H_1: P_{\text{resp}} \geq 0.60 \text{ AND } P_{\text{tox}} \leq 0.10$

In a single stage design, 20 participants will be evaluated for clinical response and toxicity. Toxicity will be defined as: unacceptable toxicities as defined in [Section 10.1](#). All unacceptable toxicities that are possibly, probably, or definitely attributed to protocol therapy will be counted as a toxicity.

The null hypothesis will be rejected if there are at least 9 responders, and no more than 3 participants who experience unacceptable toxicities. This design has power of 0.82 and a significance level of 0.11. The planned accrual rate will be one participant per month.

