10.7 Evaluation of Response

All participants included in the study must be assessed for response to treatment, even if there are major protocol treatment deviations or if they are ineligible. Each participant will be assigned one of the following categories: 1) complete response, 2) partial response, 3) stable disease, 4) progressive disease, 5) early death from malignant disease, 6) early death from toxicity, 7) early death because of other cause, or 9) unknown (not assessable, insufficient data).

All of the participants who met the eligibility criteria (with the possible exception of those who received no study medication) will be included in the main analysis of the response rate. Participants in response categories 4-9 will be considered to have a treatment failure (disease progression). Thus, an incorrect treatment schedule or drug administration does not result in exclusion from the analysis of the response rate.

All conclusions will be based on all eligible participants. Sub-analyses may then be performed on the basis of a subset of participants, excluding those for whom major protocol deviations have been identified (e.g., early death due to other reasons, early discontinuation of treatment, major protocol violations, etc.). However, these sub-analyses will not serve as the basis for drawing conclusions concerning treatment efficacy, and the reasons for excluding participants from the analysis will be clearly reported. The confidence intervals will also be provided.

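### Sections 9.0 and 10.7 define different sets for the primary response rate, and the 20 evaluable participants of 10.2 leave no room for losses under the enrolment cap of 20 in 3.3.1

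*Combined protocol and SAP*

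**What the plan says.** Four places bear on who is counted for response.

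- **Section 9.0, evaluable for objective response.** Only participants with measurable disease at baseline who "have received at least two cycles of therapy, and have had their disease re-evaluated will be considered evaluable for response". A note adds: "Participants who exhibit objective disease progression prior to the end of Cycle 1 will also be considered evaluable". The same paragraph defines the primary efficacy endpoint as the CR or PR rate after two or more cycles, and ends: "Participants with KS which progress prior to the end of Cycle 2 will be considered to have treatment failure".
- **Section 10.7.** On the main response analysis: "All of the participants who met the eligibility criteria (with the possible exception of those who received no study medication) will be included". Categories 4 to 9, which include early death from any cause and not assessable, are treatment failures. All conclusions rest on all eligible participants. Analyses that leave out, for example, those who discontinued early are sub-analyses and cannot support the efficacy conclusion.
- **Section 10.2.** "A total of 20 evaluable participants will be enrolled". The null hypothesis is rejected with at least 9 responders and no more than 3 participants with unacceptable toxicity; stated power is 0.82 and the significance level 0.11.
- **Section 3.3.1.** "This study will enroll a minimum of 6 participants and a maximum of 20 participants". Table 12-A also totals 20.

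The plan contains no replacement rule, no allowance for non-evaluable participants and no cut-off for a number other than 20.

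**The concern.** Take a participant who stops in Cycle 1 because of toxicity, withdrawal or a death not due to KS. Under 9.0 this person leaves the response denominator; under 10.7 the same person is a failure. Section 10.2 uses the word evaluable, which is the term defined in 9.0, but does not point to either section. Two analysts could each follow the protocol and report different primary response rates and confidence intervals from the same data.

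The 9.0 set also conditions on having tolerated and stayed on the drug for two cycles, so it favours the drug whenever early stoppers respond less often than the rest. Section 9.0 is uneven within itself as well: progression in Cycle 1 is expressly evaluable, whereas progression in Cycle 2 is called treatment failure but is not covered by the evaluability note.

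Finally, a requirement for 20 evaluable participants and a maximum enrolment of 20 can both be met only if nobody is lost. The plan does not say which gives way. The minimum of six participants in 3.3.1 matches no rule in a single-stage design.

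**Working it through.** **Inputs.** From Section 10.2: n = 20, at least 9 responders, at most 3 toxicities, null rates 0.30 and 0.30, alternative rates 0.60 (response) and 0.10 (toxicity). The documents give no early drop-out rate, so 5–20% is assumed. Early drop-outs are assumed never to respond unless stated otherwise.

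**1. The plan's own figures.** Exact binomial with R responders and T toxicities:

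- P(R ≥ 9 | 20, 0.30) = 0.1133; P(R ≥ 9 | 20, 0.60) = 0.9435
- P(T ≤ 3 | 20, 0.30) = 0.1071; P(T ≤ 3 | 20, 0.10) = 0.8670
- Power with independent endpoints = 0.9435 × 0.8670 = 0.818, the stated 0.82
- The null is an either/or region, so the largest type I error is max(0.1133, 0.1071) = 0.113, the stated 0.11

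The design arithmetic is right for 20 participants in both counts.

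**2. Reported rate.** Assume 3 of 20 are non-evaluable under 9.0 and there are 9 responders. Exact (Clopper–Pearson) 95% intervals:

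| Set | Rate | 95% CI |
|---|---|---|
| Section 9.0 | 9/17 = 52.9% | 27.8–77.0% |
| Section 10.7 | 9/20 = 45.0% | 23.1–68.5% |

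**3. Type I error with enrolment stopped at 20.** The cut-off is a count. Removing non-responders from the denominator cannot create a ninth responder. With a true rate of 0.30 among all treated, the number of responders is Bin(20, 0.30) under either section, and the response-side error stays 0.113.

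**4. Type I error if non-evaluable participants were replaced.** With drop-out d, the rate among evaluable participants is 0.30/(1 − d), and 20/(1 − d) must be enrolled (rounded up):

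| d | Enrolled | Rate among evaluable | P(R ≥ 9 of 20 evaluable) | P(R ≥ 9 of all enrolled), rate 0.30 |
|---|---|---|---|---|
| 10% | 23 | 0.333 | 0.19 | 0.229 |
| 15% | 24 | 0.353 | 0.25 | 0.275 |
| 20% | 25 | 0.375 | 0.32 | 0.323 |

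Every row exceeds the cap of 20. The excess comes from replacement against an unchanged cut-off and appears with either denominator.

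**5. Power.** This depends on the population to which 0.60 refers.

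- *All 20 treated:* responders are Bin(20, 0.60) and joint power stays 0.818.
- *Evaluable participants only:* the rate among the 20 treated is 0.60 × (1 − d). Joint power is P(R ≥ 9 | 20, 0.60(1 − d)) × 0.8670:

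| d | Rate among treated | Joint power |
|---|---|---|
| 5% | 0.57 | 0.784 |
| 10% | 0.54 | 0.736 |
| 15% | 0.51 | 0.673 |
| 20% | 0.48 | 0.596 |

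**The case against.** The strongest reply is that Section 10.7 already settles the matter. It names the main response analysis, counts the non-assessable as failures, bases all conclusions on all eligible participants, and demotes analyses that drop early discontinuations. This carries weight, and it is why the remedy is short. It does not close the gap: 9.0 is worded exclusively, sits in the paragraph that defines the primary efficacy endpoint, and is nowhere made subordinate; 10.2 then uses its term.

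A second reply is that the decision rule is a count, so the denominator hardly matters for go/no-go. With 20 enrolled and no replacement, that stands. An exception is a response documented in someone who received fewer than two cycles. Tumour assessment takes place on Day 1 of each cycle and at treatment discontinuation, so this can happen; such a person is not evaluable under 9.0 but has a response category under 10.7.

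A reader might infer more: that the trial's type I error is inflated, or that the contradiction costs power. The documents do not support either. Inflation needs more than 20 enrolled, which 3.3.1 forbids and no replacement rule permits. The power loss in step 5 comes from drop-out combined with one reading of 0.60, and it would be the same if 10.7 were followed without question. The unexplained minimum of six has no shown effect on the decision rule.

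**Conclusion.** The conflict between 9.0 and 10.7 is real and affects the primary response rate and its confidence interval. With an assumed three non-evaluable participants and nine responders the difference is about 8 percentage points (52.9% against 45.0%), in the drug's favour under 9.0. The go/no-go result is usually the same under both sections while enrolment stops at 20. The stated 0.11 would be exceeded only through replacement beyond the cap (0.19–0.32 at an assumed 10–20% drop-out). The stated 0.82 stands if 0.60 is the rate among all treated; otherwise it is 0.74 at 10% and 0.67 at 15% drop-out. These figures rest on assumed drop-out rates, on early stoppers not responding and, for power, on independence of response and toxicity. This is a correction worth making before analysis, but it does not invalidate the design.

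**What to change.** - **Section 9.0:** state that the two-cycle evaluable set is supportive only. State that the Section 10.7 set is primary for the nine-responder rule, the response rate and its confidence interval: eligible participants who received any dose, with those not assessable, or off treatment without a documented response, counted as non-responders.
- **Section 10.2:** replace the 20 evaluable with 20 eligible treated participants, and state that 0.60 and 0.30 refer to all of them. Alternatively, restate power with an assumed early drop-out.
- **Section 3.3.1:** align the number with 10.2, remove the minimum of six, and state that early stoppers are not replaced. Say also how a participant treated but later found ineligible is handled, since 10.7 foresees that case.

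The cost is amendment wording and a slightly less favourable reported rate or stated power. Early stoppers need no replacement, so the fix adds no participants on their account.
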